#### 5.7.4. Subject randomization

At Visit 2, an investigational center staff member will assign study medication to eligible subjects by selecting an appropriate Subject Kit. The staff member must select Subject Kits in chronological sequence and in ascending numerical order starting with the lowest available Subject Kit number.

No Subject Kit number may be omitted or reused. The Subject Kit number is the randomization number.

The sequence of study medication assignments will be assigned in a random manner in a 1:1:1 ratio.

The investigational center staff member randomizing the subject will enter the SN, subject initials and date randomized on both parts of the Subject Kit label, remove the tear-off part, attach it to the subject's Label Page CRF and record the Subject Kit number in the subject's CRF.

# 5.7.5. Dispensing study medication

The study medications must be applied only to study subjects, only at the investigational center and only by authorized personnel as required by applicable regulations, guidelines and protocol.

At Visit 2, after a subject is randomized (Section 5.7.4), locate the appropriate Subject Kit and the study medication vial with the lowest vial number. Enter the SN and date of application on the vial label.

At Visit 4, perform a retreatment application if the target lesion meets the retreatment criteria (Section 5.7.6). Locate the appropriate Subject Kit and the unused study medication vial with the lowest number and enter the SN and date of application on the vial label. Use a different vial from the vial used for the Visit 2 applications.

## 5.7.6. Study medication application

The study medications are for external, topical use on the target lesions on the appropriate study subject only.

The investigational center staff member performing the study medication applications must comply with the study medication handling warnings Section 5.7.1

At Visit 2, the staff member will perform an initial study medication application for the target lesion.

At Visit 4, if the target lesion has a PLA grade of >0 it must receive a retreatment study medication application UNLESS either of the following criteria apply to the target lesion:

- The target lesion has a Visit 4 pre-application LSR grade of 3 (severe) for any sign or symptom AND the grade has increased compared to the Visit 3 grade
- The target lesion is, in the investigator's opinion, not appropriate for a retreatment (the investigator must note the reason on the subject's Comments CRF page).

The Visit 4 retreatment applications will be terminated for all subjects in the study if 3 or more subjects in a treatment group discontinue from the study due to study medication related AEs. The Aclaris Therapeutics Medical Monitor will inform each investigator if this situation occurs.

To perform a study medication application for a target lesion the staff member will select the appropriate vial of study medication (Section 5.7.5) then follow these application instructions:

- Wash her/his hands prior to, and after completing the study medication applications
- Wear latex, nitrile or vinyl examination gloves during the application
- DO NOT EVER pass the study medication vial or any study medication applicator over the subject's body or face even if the vial is closed and the applicator is dry.
- Do not apply the study medications to eyes, mouth, mucous membranes, open wounds
- Do not apply the study medication to the eyelids or within 5 mm of the orbital rim

- If, in the investigators opinion it is needed to ensure no study medication enters the eye:
  - Position the subject in the supine position with the head slightly elevated and angled such that any excess study medication will flow away from the eye.
  - Apply white petrolatum (100%) United States Pharmacopeia (USP) along the orbital rim and at the medial and lateral canthi; gently stretch the periorbital skin between the thumb and forefinger at the time of petrolatum application to distend any periorbital rhytides (*e.g.*, "crow's feet") and ensure full coverage of the skin at the base of the rhytides to decrease the likelihood of tracking of the study medication towards the eye
  - Have the subject hold an absorbent pad in the appropriate area of the eye to absorb any excess study medication that might track away from the target lesion
  - Instruct the subject to keep both eyes closed during the entire study medication application procedure
- After the subject is properly prepared and positioned, thoroughly cleanse the target lesion by firmly rubbing with a cotton-tipped swab or absorbent wipe wetted with 70% isopropyl alcohol
- Hold the study medication vial away from her/his face and from the subject's face when opening and at all times
- Using the supplied applicator:
  - Wet the applicator with a quantity of study medication sufficient to wet the target lesion with a thin film
  - Using firm pressure and an application technique that is appropriate for the target lesion size (*e.g.*, dab and roll the applicator on smaller lesions; rub using a circular motion on larger lesions) apply the study medication to the target lesion for approximately 20-30 seconds
  - Minimize exposure to the surrounding normal skin and sensitive areas; you may have the subject assist by holding absorbent material (*e.g.*, clean absorbent wipe, clean paper towel, etc.) to prevent the study medication from migrating from the target lesion
  - During the application process remove excess study medication from the surrounding skin using a clean absorbent wipe
  - Ensure the target lesion is wet with study medication at the end of the 20-30 seconds
  - $\circ\,$  Allow the target lesion to remain undisturbed for approximately 60 seconds
  - o After approximately 60 seconds repeat the application process
  - Repeat the application/waiting cycle until the study medication has been applied to the target lesion 4 times.

Record the time the final application to the target lesion is completed as the Application Completion Time.

After completing the study medication application to the target lesion do not disturb the target lesions until just prior to the subject's post-application LSR evaluation (Section 6.2.1). Just prior to the subject's post-application LSR evaluation (Section 6.2.1) absorb any remaining study medication, dry the target lesion without wiping or rubbing and after the target lesion and surrounding area are confirmed to be dry, remove, by gently wiping, any white petrolatum that may remain.

An eyewash kit is provided to use in the event that study medication comes in contact with a subject's eye. Follow the instructions on the eyewash kit to cleanse both of the subject's eyes. If you use the eyewash kit the event must be reported as an adverse event of "eye irritation" (Section 7.1.1).

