#### 7.1. Definitions

#### 7.1.1. Adverse events (AE)

An AE is any untoward medical occurrence in a patient or clinical investigation subject administered a study medication(s) and which does not necessarily have a causal relationship with the study medication. An AE can therefore be any unfavorable and unintended sign or symptom associated with the use of a study medication (including an abnormal laboratory finding), whether or not related to the study medication.

Thus any new, clinically relevant worsening of an existing sign, symptom or disease, should be considered an AE.

Worsening of any of the target lesion assessments should be reported as an AE ONLY if the use of the study medication is interrupted or discontinued or if therapy is required to manage the event.

The investigator must, for any AE associated with a target lesion, question the subject in detail to determine if there are any confounding factors (*e.g.*, irritation by clothing or activity, sunburn) for any such AE.

Report any event that requires use of the eyewash kit [Section 5.7.6] as an AE for "eye irritation". For all AEs of this type:

- Contact the medical monitor (see contact information on Page 1, or in Section 7.2.2) immediately (within 24 hours)
- Unblind the study medication for the subject (Section 5.10.2)
- Arrange for the subject to be transported to the most appropriate hospital emergency room (ER) and provide the study medication identification information to the appropriate ER staff
- Follow the course of the AE
- Report the event as an SAE if appropriate (Section 7.1.2).

Every new episode or clinically relevant worsening of a chronic condition (*e.g.*, headaches, seasonal allergies, depression, and hypertension) should be reported as a separate AE, even if the condition is reported in the subject's medical history.

The investigator should, when certain, report a diagnosis rather than the signs, symptoms or clinically relevant abnormal laboratory values associated with the AE. Otherwise, signs, symptoms or abnormal laboratory values may be used to describe the AE.

Any CR abnormality discovered prior to the first study medication application should be reported as medical history, not as an AE.

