## 7.1.3. Unexpected adverse event

An AE is considered unexpected if it is not listed in the Investigator Brochure or is not listed at the specificity or severity that has been observed.

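### Every eyewash use must be reported as the adverse event 'eye irritation' whatever was found, so a symptom-free contact is recorded like true mild irritation and a specific eye diagnosis may get a generic term

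*Combined protocol and SAP*

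**What the plan says.** The rule on the term appears twice in the combined protocol and SAP.

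- Section 5.7.6 (study medication application): "An eyewash kit is provided to use in the event that study medication comes in contact with a" subject's eye. It continues: "If you use the eyewash kit the event must be reported as an adverse event of" *eye irritation*.
- Section 7.1.1 (adverse events): "Report any event that requires use of the eyewash kit [Section 5.7.6] as an AE for" *eye irritation*. For all AEs of this type it then requires contact with the medical monitor within 24 hours, unblinding, transport to an emergency room and follow-up of the event. It adds: "Report the event as an SAE if appropriate".

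Three other provisions bear on how such an event is recorded and reported.

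- Section 7.1.1 also has a general rule on terms: "The investigator should, when certain, report a diagnosis rather than the signs, symptoms or clinically relevant abnormal laboratory values associated with the AE".
- Section 7.1.5 grades every AE as mild, moderate or severe. Mild, the lowest grade, presupposes that a sign or symptom is noticed.
- Section 9.2 summarises AEs by study medication as proportions overall and by MedDRA System Organ Class, with listings of incidence within each class. It names no ocular table and no split by severity, seriousness or relationship.

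**The concern.** An AE term should describe what happened to the subject. Here it is set by the use of a piece of equipment. Two kinds of error can follow. A contact that produced no sign or symptom enters the database as irritation, which overstates ocular harm. A contact that produced a specific, diagnosable eye condition may enter under the same generic word, which under-describes the harm.

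The study's rationale is safety and efficacy on the face, and 5.7.6 gives considerable space to keeping the solution away from the eye. Ocular events are therefore among those a reader of the safety results will look for. With about 36 subjects per group, any such events are likely to be read one by one, so the accuracy of each record matters more than a rate.

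**Working it through.** The plan states no figure on this point, so there is none to reproduce. The check sets the provisions side by side.

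**Step 1: trigger.** In 5.7.6 the kit is for contact with the eye, and its use creates the AE. No sign or symptom is required. Section 7.1.1 speaks of an event that requires the kit, which is slightly narrower than use of the kit. Neither section makes an exception for a contact without findings or for a diagnosed injury.

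**Step 2: what each kind of event would carry.**

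| Event after eye contact and rinse | Term under the eyewash rule | Term under the diagnosis rule in 7.1.1 | Severity under 7.1.5 | Separable in the record? |
|---|---|---|---|---|
| A. Nothing found | eye irritation | nothing to diagnose | no grade fits; mild is nearest | Not from B |
| B. True mild irritation | eye irritation | eye irritation | mild | Not from A |
| C. Specific diagnosis, neither severe nor serious | eye irritation | the diagnosis | mild or moderate | Only by grade or follow-up detail, or if a further AE is entered |
| D. Severe or serious injury | eye irritation | the diagnosis | graded on its merits; SAE if appropriate | Yes, by severity, SAE status and follow-up |

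In rows C and D the two rules of 7.1.1 give different terms, and the section does not say which prevails. In row A the severity scale has no place for the event.

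**Step 3: what the planned summaries show.** Under 9.2, all four rows add one subject to the overall AE proportion and one to whichever System Organ Class the term is coded to. If the listings within each class show the term, it is the preset one. The fields that separate D from A are collected but are not named in any planned display. This loss comes from the choice of summaries as well as from the fixed term.

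**Step 4: scale, as illustration only.** Input: about 36 subjects per group (Section 4.1). Assumption: 0 to 3 eyewash uses in a group, since the documents give no count. The proportion is k/36, with exact (Clopper-Pearson) 95% limits.

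| k | k/36 | 95% limits |
|---|---|---|
| 0 | 0% | 0% to 9.7% |
| 1 | 2.8% | 0.07% to 14.5% |
| 2 | 5.6% | 0.7% to 18.7% |
| 3 | 8.3% | 1.8% to 22.5% |

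One symptom-free contact moves a group's proportion by 1/36 = 2.8 percentage points, well inside the uncertainty of any such estimate.

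**The case against.** The strongest reply is that the record holds far more than the term. Each AE has a severity grade and a relationship. Eyewash events are notified, followed and reported as SAEs where appropriate. Section 5.10.2 requires the reason for unblinding to be recorded and an unblinded subject to be discharged, so each case can be traced. Nothing forbids a second or updated AE term. Capturing every contact is also a defensible, conservative safety aim, because accidental contact that leads to an emergency room can reasonably be called untoward.

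Most of this stands. It defeats the inference that the data cannot tell a trivial rinse from an eye injury: a severe or serious injury can be identified. It does not help with a symptom-free contact and true mild irritation, which share term and grade. Nor does it settle which rule governs the term when a diagnosis is certain. Full capture can be kept without calling every contact irritation.

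Three other stronger readings are tempting, and the documents do not support them.

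- **That an ocular safety table will be distorted.** Section 9.2 plans no such table.
- **That the preset term makes unexpected events look expected.** Section 7.1.3 calls an event unexpected if it is absent from the Investigator Brochure or "is not listed at the specificity or severity that has been observed". That test turns on what was observed, not on the label, and the brochure is not among the documents.
- **That a harmless rinse on vehicle would cancel an injury on active treatment.** Such a pair can be constructed (1/36 against 1/36), but no event count in the documents makes it more than hypothetical.

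**Conclusion.** The concern holds as a defect of recording. Followed as written, 5.7.6 and 7.1.1 count a symptom-free eye contact as an eye AE that cannot be separated from true mild irritation. They also leave open whether a specific eye diagnosis is reported as such or under the generic term. The first effect follows directly from the text. The second depends on how sites resolve two instructions with no stated order of precedence, so it is a risk and not a certainty.

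The size is modest. No sample size, test or other stated figure is affected, safety analysis is descriptive, and the 2.8% per event is illustration resting on 36 subjects per group and an assumed count. The conclusion assumes that CRF pages not included in the documents do not already hold a separate field for eye contact. The point is worth correcting because the remedy is cheap and ocular exposure is a hazard the protocol itself singles out.

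**What to change.** 1. Reconcile 5.7.6 and 7.1.1 so that each eye contact or eyewash use is recorded as its own CRF item, whatever the finding. Align the two wordings of the trigger (use of the kit, and an event requiring it).
2. Let the AE term be the diagnosis, or the sign or symptom where there is no diagnosis, that was actually found. Where nothing was found, the exposure item carries the record.
3. Tie the existing notification, unblinding and care steps in 7.1.1 explicitly to eyewash use. They now hang on AEs of this type, so changing the term alone would remove their stated trigger for a contact without findings. The steps themselves stay as they are.
4. Add to 9.2 a listing of eyewash events by arm, with finding, severity, seriousness and outcome.

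The cost is one CRF item, one listing and a small redraft of 5.7.6 and 7.1.1, plus the line in 9.2. No visit or procedure is added, and every exposure is still captured.

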# 5.7.7. Dose compliance record

At every study visit where a study medication application is performed, an investigational center staff member will document the study medication usage in the CRF.

## 5.7.8. Dose modification

Study medication applications will be performed at Visit 2, and if appropriate Visit 4, by the investigator or an investigational center staff member at the direction of the investigator. No study medication will be dispensed to the study subjects.

If any subject refuses to allow the initial study medication treatment or a retreatment application, the investigator must report the visit number, visit date and the reason for the refusal on the subject's Comments CRF page.

If the subject's refusal is associated with an AE, the investigator must report the event on the appropriate CRF (Section 7.2).

The subject must have the initial study medication application to the target lesion to remain in the study.

The subject does not need to be removed from the study based solely on her/his refusal to have a study medication retreatment application on the target lesion.

# 5.8. Study medication Management

## 5.8.1. Accountability

The investigator or designee will maintain an accurate record of the receipt of the study medications as shipped by Aclaris Therapeutics, Inc. (or designee), including the date received and the condition of the study medications. One copy of this receipt will be returned to Aclaris Therapeutics, Inc. (or designee) when the contents of the study medication shipment have been verified and one copy maintained in the study file. In addition, an accurate study medication disposition record will be kept, specifying the amount dispensed for each subject and the date of dispensing. This inventory record will be available for inspection at any time. At the completion of the study, the original inventory record will be available for review by Aclaris Therapeutics, Inc. upon request.

## 5.8.2. Return and disposition of study supplies

At the completion of the study, all used and unused study medication vials will be returned to Aclaris Therapeutics, Inc. (or designee) for disposal per Aclaris Therapeutics, Inc. (or designee's) written instructions.

## 5.9. Other Study Supplies

Aclaris Therapeutics, Inc. will provide:

- Handheld mirrors to assist the subject with the SSA
- An appropriate ruler, or other instrument, for measuring the lesion dimensions
- 70% isopropyl alcohol for cleansing the SK target lesions during the study medication application process
- White Petrolatum USP for protecting sensitive areas during the study medication application
- Templates for identifying target lesions
- Supplies and instructions for collecting, labeling, shipping and result reporting for the clinical laboratory tests and urine pregnancy tests from a third party
- For one selected investigational center only, equipment, supplies and training for taking standardized photographs from a third party
- Eyewash kits.

## 5.10. Blinding

## 5.10.1. Verification of blinding

Blinding of the study medications is important for validity of this study. This study uses a double-blind design. The study medications are indistinguishable in appearance, packaging and labeling.

## 5.10.2. Un-blinding during the study medication

Blinding is important for validity of this clinical study. However, the blind may be broken in the event of a medical emergency, in which knowledge of the study medication identity is critical to the management of the subject's course of treatment. Before breaking the blind the investigator should determine that the information is necessary (*i.e.*, that it will alter the subject's immediate course of treatment). In many cases, particularly when the emergency is clearly not study medication-related, the problem may be effectively managed by assuming that the subject is receiving an active study medication without the need for un-blinding.

If deemed necessary to break the blind for a study subject, attempt to contact the Aclaris Therapeutics, Inc. Medical Monitor (protocol page 1 and Section 7.2.2) to obtain concurrence. If it is not possible to contact the Medical Monitor beforehand, contact her/him as soon as possible after breaking the blind for a subject.

To identify a subject's study medication, locate the second panel of the tear-off label attached to the subject's Label Page CRF and follow the instructions on the label. Record the date of un-blinding, the reason for un-blinding and the initials of the investigational center staff member who performed the un-blinding on the subject's Label Page CRF.

Any subject whose blind has been broken must be discharged from the study (Section 4.6).

At the end of the study, the original Label Page CRFs will be returned to Aclaris Therapeutics with a photocopy placed in the investigator's study file. The original Label Page CRFs will be available, upon request, to the site if needed to respond to a regulatory audit.

Any event that requires the use of an eyewash kit the investigator is required to break the blind for the subject and take appropriate action (Section 7.1.1).

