## 4.6. Subject Discontinuation from the Study

Subjects will be informed that they are free to withdraw from the study at any time and for any reason.

The investigator may remove a subject from the study if, in the investigator's opinion, it is not in the best interest of the subject to continue the study. Examples of other reasons subjects may be discontinued from the study are a change in compliance with an inclusion or exclusion criterion, occurrence of AEs, occurrence of pregnancy or use of a prohibited therapy. Immediately (within 24 hours) notify the Aclaris Therapeutics, Inc. study monitor of discontinuation.

In case of premature discontinuation of study participation, efforts will be made to perform all final study day assessments. The date the subject is withdrawn from the study and the reason for discontinuation will be recorded on the subject's case report forms (CRFs). All withdrawn subjects with ongoing AEs will be followed as appropriate (Section 7.2.1).

The study may be discontinued at the discretion of Aclaris Therapeutics, Inc. Some examples of reasons for discontinuation are the occurrence of the following:

- Increased frequency, severity or duration of known AEs
- Medical, regulatory or ethical reasons affecting the continued performance of the study
- Difficulties in the recruitment of subjects.

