# 9. STATISTICAL ANALYSES

## 9.1. Statistical Analysis of Clinical Indices

The primary effectiveness analysis will consist of mean change from baseline to Visit 8 PLA performed using Analysis of Covariance (ANCOVA) with baseline PLA as the covariate. The analysis will be performed at each post-baseline visit with emphasis on Visit 8. Comparisons between vehicle and each active treatment group will be performed within the model using least-squares means and the common error term. The primary efficacy analyses will be based on the per protocol (PP) population, defined as all randomized subjects who completed the study with no major protocol violation.

A secondary efficacy analysis of a separate comparison between each active treatment group and the vehicle treatment group based on the proportion of subjects whose target lesion is judged to be clear on the PLA (PLA = 0) at Visit 8. A separate Cochran-Mantel-Haenszel (CMH) test stratified by Site will be used for each comparison. A secondary efficacy analysis will also be conducted using this same methodology, but based on SSA.

Secondary analyses will initially be performed on the PP population, but will also be performed on the intent-to-treat (ITT) population defined as all randomized subjects with non-missing data at baseline and at least one post-baseline visit. As a secondary analysis, the primary efficacy analysis will be performed using the ITT population. For all ITT-population analyses, missing efficacy data will be imputed from the last non-missing post-baseline visit carried forward to subsequent missing visits (LOCF).

For all analyses, two-tail alpha will be set to 0.05 with no adjustment for multiple comparisons. ANCOVAs will include Site in the model if doing so improves the sensitivity of the model for comparing treatment groups. As a sensitivity analysis, the primary efficacy analysis will also be run including Site and the Treatment-by-Site interaction. If the interaction term is associated with p < 0.10 then treatment group means for each Site will be examined individually to understand potential site differences. Sites with less than two completed blocks of subjects will be pooled with other such Sites to achieve new pooled analysis Sites that meet this criterion. Sites will

first be ranked by sample size and then pooled in that order until each new pooled analysis Site meets the two-block threshold.

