### 9.2. Statistical Analysis of Safety Data

Descriptive statistics will be calculated on the safety parameters using the ITT population. The proportion of subjects with treatment-emergent adverse events will be tabulated and presented by treatment and Medical Dictionary for Regulatory Activities (MedDRA) System Organ Class. Vital signs, LSR scores and clinically relevant abnormal laboratory results will also be tabulated and presented by study medication. No inferential testing will be performed.

Data from all randomized subjects will be presented and summarized. Safety summaries by study medication group will include listings by study medication of adverse events incidences within each MedDRA System Organ Class, and changes from pre-application values in vital signs. Adverse event summaries will be presented by study medication showing the proportion of subjects experiencing adverse events, both overall and by MedDRA System Organ Class.

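### Eyewash use leads by rule to unblinding and discharge, so a treated subject leaves the primary analysis and, if it happens at Visit 2, may also leave ITT and the ITT-based safety statistics

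*Combined protocol and SAP*

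**What the plan says.** Two rules in Section 5.10.2 act in sequence. On eyewash use: "Any event that requires the use of an eyewash kit the investigator is required to break the blind for the subject". On what follows: "Any subject whose blind has been broken must be discharged from the study". Section 7.1.1 repeats the unblinding instruction for these events and adds hospital referral and follow-up of the event itself.

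The discharge sentence points to Section 4.6, which says: "In case of premature discontinuation of study participation, efforts will be made to perform all final study day assessments". The same section provides for follow-up of withdrawn subjects whose adverse events are still ongoing.

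Section 9.1 limits the primary PP population to completers without a major violation. The ITT population is "defined as all randomized subjects with non-missing data at baseline and at least one post-baseline visit", with LOCF of post-baseline values.

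Section 9.2 opens with: "Descriptive statistics will be calculated on the safety parameters using the ITT population". Its second paragraph then promises summaries covering everyone who was randomized. Section 4.8 rules out replacing non-completers.

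**The concern.** Section 5.10.2 otherwise tells the investigator to unblind only when the result would change immediate care. Eyewash use is the exception: unblinding is compulsory, and the end of participation follows from it. The loss of follow-up is therefore produced by the protocol and not by the subject's wishes or the state of the lesion.

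Safety and efficacy on the face are a stated objective. The rule removes subjects with the one facial exposure event for which the protocol writes a dedicated procedure. Two things are at stake. One is whether a treated subject, and the event that ended participation, appear in the safety statistics. The other is whether the ITT analysis has a usable Visit 8 outcome for that subject.

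**Working it through.** **Tracing one eyewash case through the analysis sets.** Study medication is applied only at Visits 2 and 4. PLA is graded before application at both (Section 6.1.2). SSA is collected only at Visits 2 and 8 (Section 6.1.1). I assume that discharge takes place before the next scheduled visit.

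| | Event at Visit 2 (Day 1) | Event at Visit 4 (Day 22) |
|---|---|---|
| PP (primary) | Out: not a completer | Out: not a completer |
| ITT | Out, unless an early final assessment counts as a post-baseline visit | In, through the Visit 3 LSR and the pre-application Visit 4 PLA |
| PLA value carried to Visit 8 | None; or a Day 1 post-application grade if the early assessment counts | The pre-application Visit 4 grade, unless an early final PLA is taken |
| SSA at Visit 8 | Missing, unless assessed early | Missing, unless assessed early |
| Safety, first sentence of 9.2 (ITT) | Follows ITT status | In |
| Safety, second paragraph of 9.2 (all randomized) | In | In |

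The 10- and 20-minute LSR readings on Day 1 belong to Visit 2 itself, so on a plain reading they do not supply a post-baseline visit. The 20-minute reading covers four signs only (erythema, edema, scaling/dryness, vesicles/bullae; Section 6.2.1). Erosion, ulceration, pigment change and scarring are next scheduled at Visit 3.

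**Reproducing the plan's power.** Inputs from Section 9.3: 32 completers per arm, clear rates p1 = 0.325 and p2 = 0.031, two-sided alpha 0.05, stated power about 87%. The formula is power = Φ[(p1 − p2 − 1.96·SE0)/SE1], where SE0 uses the pooled proportion.

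- Pooled p = (0.325 + 0.031)/2 = 0.178; SE0 = √(0.178 × 0.822 × 2/32) = 0.0956.
- SE1 = √[(0.325 × 0.675 + 0.031 × 0.969)/32] = 0.0883.
- Power = Φ[(0.294 − 0.1874)/0.0883] = Φ(1.207) = 0.886.

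Fisher's exact test by enumeration gives 0.852. The stated 87% lies between the two, so it is reproduced.

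**Effect of losing k active subjects from PP** (32 − k against 32, same formula):

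| k | 0 | 1 | 2 | 3 | 4 |
|---|---|---|---|---|---|
| Power | 0.886 | 0.882 | 0.877 | 0.872 | 0.867 |

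The synopsis already allows for 108 − 96 = 12 non-completers, or 4 per arm. The k losses above would be on top of those.

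**Effect on the clear rate** (secondary endpoint). Suppose k of 36 subjects in an arm have unknown outcome and the rest clear at 0.325. The arm's rate then lies between 0.325(36 − k)/36 and [0.325(36 − k) + k]/36.

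- k = 1: 0.316 to 0.344
- k = 2: 0.307 to 0.363
- k = 3: 0.298 to 0.381

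**How many events.** The documents give no rate. With an assumed rate q per subject, the expected number per arm is 36q. The chance of three or more in a given arm is the binomial tail.

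| Assumed q | 1% | 2% | 5% | 10% |
|---|---|---|---|---|
| Expected per arm | 0.36 | 0.72 | 1.8 | 3.6 |
| P(3 or more in an arm) | 0.6% | 3.5% | 26.8% | 71.2% |

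Three matters because Section 5.7.6 ends retreatment for the whole study once three or more subjects in a group discontinue for related adverse events. The documents do not say whether a discharge forced by unblinding counts.

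**The case against.** Discharge after unblinding is a defensible, conservative choice when the endpoint is graded by an investigator whose site has opened the label. The event itself is not abandoned: Section 7.1.1 says "Follow the course of the AE", Section 7.2.1 follows related events to resolution or a stable outcome, and Section 4.6 asks for final assessments. The trigger is use of the kit, which is supplied for eye contact with solutions of identical appearance. Lesion-location limits and the eye-protection steps should keep it uncommon. All of this stands. It does not restore scheduled lesion follow-up, and an effort to assess a subject on the day of hospital referral is a weak substitute for Day 106.

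Three stronger readings are tempting, and the documents do not support them.

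- A reader might infer that every eye event removes a subject from every analysis set, including safety. The trigger is narrower than that, a Visit 4 case remains in ITT and safety, and the second paragraph of Section 9.2 would keep even a Visit 2 case in the safety summaries. What exists is an unresolved contradiction.
- A reader might infer that a Visit 2 subject is both lost from ITT and given a carried-forward Day 1 grade. These are alternatives; which one applies depends on a rule the plan does not state.
- A reader might infer bias between arms. Nothing in the documents shows that eye contact is more likely on active solution or related to clearing.

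**Conclusion.** The point holds in a limited form and is a cheap improvement. Any eyewash case loses PP status and later scheduled follow-up. Only a Visit 2 case can also fall outside ITT, and its place in the safety statistics depends on which statement in Section 9.2 governs. If its early assessment is counted, LOCF puts a Day 1 grade where a Day 106 outcome belongs.

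The expected effect on power is small: about 1.4 percentage points for three active subjects lost (0.886 − 0.872). The clear-rate limits are worst cases for the secondary endpoint and do not estimate bias in the primary mean PLA change. All counts of one to three events, and the 1% to 10% rates, are assumptions. The case rests on the safety denominator and on avoidable loss of outcome data.

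**What to change.** 1. **Section 9.2.** Reconcile the two statements by basing safety summaries on all randomized subjects who received study medication, whether or not they have a post-baseline visit.
2. **Section 5.10.2.** Replace mandatory discharge with continued scheduled no-treatment assessments through Visit 8 (PLA, SSA, LSR, adverse events) where the subject agrees. Record the unblinding, include the subject in ITT, state PP status in advance, and add one sensitivity analysis without unblinded subjects.
3. **Section 9.1.** State that a PLA graded on the same day after application is not carried forward as a Visit 8 value, and say whether an early final assessment counts as a post-baseline visit.
4. **Sections 4.6, 5.7.6, 5.10.2 and 7.1.1.** Reconcile these so that the change does not silently alter the discontinuation count in Section 5.7.6. No treatment or stopping rule is proposed here; that count is for the clinical team to settle.

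The cost is a few lines of text and one extra analysis. The downside is that a few later PLA grades come from a site that knows the arm. The sensitivity analysis shows whether they affect the result.
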